**V. POTENTIAL RISKS AND BENEFIT ASSESSMENT**

The known risks, inconveniences, or side effects from the proposed procedures in the project are shown in Table 2.

**Table 2. Potential Risks and Efforts to Minimize the Risks to Human Subjects**

Procedure	Potential Risks	Efforts to Minimize the Risks
Ethanol (alcohol) Consumption	
Alcohol intake is associated with a variety of health risks, including high blood pressure, liver disease, impaired cognitive function, weakened immune system, and certain types of cancers. Other risks include drowsiness, malaise, mood and behavior changes, depression, headaches, impaired coordination and judgment, and the potential for addiction and dependency. Drinking alcohol also increases the risk of short-term harms, including motor vehicle accidents and injuries.
	
Before enrolling in the study, several measures will be conducted to minimize risks including the following: stringent inclusion/exclusion criteria; SASSI and MAST substance abuse screening questionnaires, a diagnostic interview by a trained behavioral psychologist, and an overnight alcohol test. Additional safeguards and alcoholism screening tools will be implemented frequently throughout the duration of the study. To reduce the risks of alcohol-related harms, participants will be instructed to consume the alcohol over the course of a couple hours at home (not strictly before bedtime) and not while driving or operating machinery. Participants will also report any adverse events or undesirable changes in mood or behavior throughout the duration of the study. Participants will be monitored for non-compliance, as the consumption of additional alcoholic drinks beyond what is required for the study may exacerbate the risks associated with alcohol use.

Blood Draws (Fasting)	Bruising, bleeding, pain, and infection pose minimal risks.	Trained phlebotomists and personnel will use sterile technique.


Magnetic Resonance Imaging (MRI) and Spectroscopy (MRS)
	
There are no known biological risks associated with magnetic resonance scanning. There is a minimal risk for side effects, such as feelings of claustrophobia or muscle-skeletal discomfort from lying partially in the magnet for up to 45 minutes. There may also be loud, unpleasant noise. The magnetic field can move any metallic objects and disrupt the function of certain electronic devices that are inside the body. The long-term risk of exposure to a magnetic field is unknown, but considered extremely low.
	
Pillows will be used to ensure comfort during the testing. Earplugs or headphones are provided to reduce the noise. Certain implants, electronic devices, or any other foreign metallic objects in the body will not be permitted.

FibroScan
	
There may be minor discomfort from the application of the gel and pressure on the skin from the Fibroscan probe. However, there are no known health risks associated with the FibroScan.
	

Confidentiality of Data
	
Taking part in this research may involve providing information that one considers confidential or private. There is a slight risk that data could be revealed inappropriately or accidentally
	
Study researchers and staff will take steps to protect data that is collected. Efforts, such as coding research records, keeping research records secure and allowing only authorized people to access research records, will be made to keep the data safe. The SCID-5, SCID-NP, SASSI, and MAST data will not be stored in Medical Records. Rather, this information will be stored in locked file cabinets in the Ingestive Behavior Laboratory, which is under the directorship of [name], who will supervise the delivery of these instruments and, in collaboration with the Medical Investigator, [name], interpret the instruments.

Archive of Biological (Blood) Sample
	
The primary risk to participants who have blood banked for future research is the risk of loss of confidentiality and/or privacy. These blood samples will be stored indefinitely. The samples may be given to other investigators for future research as well. The future research may not take
	
For privacy and confidentiality, the biospecimens will be labeled with a unique series of letters and numbers. The research done with the specimens may help to develop new products in the future, or may be used to establish a cell line or test that could be

	
place at Pennington Biomedical Research Center and may not be reviewed by Pennington Biomedical Research Center's Institutional Review Board.
	
patented or licensed. Subjects will not receive any financial compensation for any patents, inventions or licenses developed from this research. Storage and disposal of biospecimens will be conducted in a manner conforming to the appropriate care and handling of biological specimens as outlined through the Institutional Biohazard Committee Guidelines.

--	--	--

**Protection Against and Minimizing Risks.** While there are some potential risks for the proposed study, the design makes every attempt to prevent the possibility of any adverse events by the activities listed in Table 2, last column. Monitoring by the experienced investigators and professionals involved in the study will minimize all potential risks. By mitigating the potential risks, the risks that are associated with the proposed procedures are less than the potential benefits to be gained by the participants.

**Potential Benefits to Human Subjects.**

Benefits. Subjects will undergo an 8-week, 30% calorie-restricted feeding intervention that will result in substantial weight loss and potential improvements in metabolic health. Participants will also receive important information about their health (i.e. adipose tissue distribution and insulin sensitivity).

Compensation for participation. After completion of the study, participants will be compensated \$250. Subjects that do not complete the entire study will be compensated \$50 for the successful completion of CV1, \$100 for the successful completion of the intervention, and \$100 for the successful completion of CV2. The total \$250 is determined according to standard policies for procedures done at PBRC.

**Data Collection, Storage and Subject Confidentiality.**

Protection of Subject Privacy and Stored Data. Protection of subject privacy will be accomplished by a variety of stringent security measures. Physical examinations will occur in an enclosed, private area. All health history and exam results will also be discussed in a private area. All medical records will be stored in locked areas, and access to these areas is limited to the clinic support staff, the Director of the clinical facilities, PIs at PBRC, and authorized designees of the PI. Volunteer medical records will be filed according to an assigned volunteer ID number. Further, the SCID-5, SCID-NP, SASSI, and MAST data will not be stored in Medical Records. Rather, this information will be stored in locked file cabinets in the Ingestive Behavior Laboratory, which is under the directorship of [name] who will supervise the delivery of these instruments and, in collaboration with the Medical Investigator, [name], interpret the instruments. This process is in place to prevent the unintended release of psychological information should a copy of a participant's medical records be requested. The only people who will know that these patients are research participants are members of the research team. No information about them, or provided by them during the research, will be disclosed to others without their written permission, except if it is necessary to protect their rights or welfare (for example, in case of injury or emergency care), or if it is required by law. When the results of the research are published or discussed in conferences, no information will be included that would reveal the identity of the individuals. Participants will be identified by codes when the data gathered in this procedure is presented or published. Authorized representatives of the NIH may

need to review records of individual participants. As a result, they may see their name; but they are bound by rules of confidentiality not to reveal the participants' identity to others. Electronic data is stored in a secured Microsoft SQL database. Only authorized IT personnel in Computing Services have access to the database.

Database Protection. Electronic data storage is secured with password protection and similarly restricted with only the PI and authorized persons having access to databases containing confidential clinical records, i.e. those containing name or other identifying information. Electronic communication will involve only unidentifiable information.

Participant confidentiality. PBRC complies with the federal 1996 Health Insurance Portability and Accountability Act (HIPAA). Specifically, PBRC protects the privacy and confidentiality of medical records and information contained in medical records of persons who are subjects of research projects, including all protected health information (PHI) as defined by the HIPAA privacy Regulations. PHI of research subjects and the use or disclosure of such information is governed by PBRC research policies as well as Common Rule, FDA regulations, and other applicable laws.

PBRC and study PIs (the persons chiefly responsible for the record) protect the privacy of research subjects and their PHI collected during a research project. PBRC will not use or disclose existing PHI or PHI created during a research project, unless the:

- Subject signs both (a) a HIPAA Authorization for use and disclosure of PHI using an approved Authorization Form or other form containing all the elements of legally effective HIPAA authorization; and (b) the informed consent to participate in research form approved by IRB; or
- IRB grants a waiver to the requirement of obtaining a signed HIPAA authorization Form, or
- IRB approved protocol uses properly de-identified PHI

All participants are assured of their anonymity and confidentiality both verbally and in the informed consent.

### **Data and Safety Monitoring Plan (DSMP)**

- Description – The DSMP has been developed to provide ongoing oversight and monitoring of the proposed study to ensure and maintain:
  - a) The scientific validity and integrity of the data so that new unbiased scientific knowledge is obtained
  - b) Protocol compliance
  - c) The safety of the participants (The study staff will remain in contact with the participants throughout the study. The participants will have the PIs' and study coordinator's work telephone number and the after-hours number to allow participants to contact them in case of an emergency.)
- Data and Safety Monitoring committee - A local group of scientists at the Pennington Biomedical Research Center (PBRC) will perform the Data and Safety Monitoring (DSM). It includes:
  - a. Members of the Investigator team:
    - i. The PIs: [name]. and [name].
    - ii. The study coordinator
    - iii. The Medical Investigator: [name].
    - iv. The Bio-Statistician: [name].
  - b. Independent individuals who are not directly involved in the study:
    - i. Independent Monitor: TBD

- Meeting structure - These meetings will be open sessions, at which all committee members will be present. The main focus will be on accrual, protocol compliance, review of lab data and review of all AEs/SAEs. No outcome results will be discussed except after completion of the data collection.
  - a. The DSM committee will meet once every 3 months. (Note: An ad hoc meeting will be held with [name] in case of a serious adverse event or death.)
  - b. Minutes will be recorded by the study coordinator and will be forwarded to all members of the committee.
  - c. The Independent Monitor will:
    - 1. Identify any deficiencies in the DSM plan and advise solutions
    - 2. Prepare a report reflecting the results of the reviews and discussion by the DSM committee.
  
- Data Quality and Management - The PI or study staff will review all data collection forms on an ongoing basis for data completeness and accuracy as well as protocol compliance.
  
- Safety Monitoring
  - a) Study risk assessment - A description of the anticipated risks (i.e. adverse events) related to the procedures and efforts to minimize the associated risks are shown in Table 2 and will be included in the consent form.
  - b) Definitions
    - Adverse events (AE) are defined as expected adverse events if they are grade 2 and above in severity and unexpected side effect/events of any severity category. An adverse finding can include a sign, symptom, abnormal assessment (laboratory test value, vital signs, electrocardiogram finding, etc.) or any combination of these.
    - Serious Adverse Event (SAE) is any adverse event that results in one or more of the following outcomes:
      - Death
      - A life-threatening event
      - Inpatient hospitalization or prolongation of existing hospitalization
      - A persistent or significant disability/incapacity
      - A congenital anomaly or birth defect
      - Important medical event based upon appropriate medical judgment
  - c) Plan for AE detection and documentation
    - Flexible monitoring via interactive contacts*
      - The study staff will remain in contact with the participants throughout the study. The participants will have the PI, Medical Investigator, and study coordinator's work telephone number and the after-hours number to allow participants to contact them with questions or in case of an emergency related to the alcohol.
    - Fixed visits*
      - At the start and end of the study, participants will come to the PBRC when routine biochemical blood tests are performed to exclude major pathology. In addition, the Medical Investigator or a designated physician's assistant will meet with the participants monthly when they

come to give blood for measurement of liver enzymes. Any out of range lab values from these tests will be recorded and reported to the PI.

*AE documentation by the study coordinator*

- Any event that is reported to either the PI or his designated research associates by the subject or medical staff caring for the subject which meets the criteria for an adverse event will be documented as such and graded as to its attribution (alcohol relatedness) and severity.
- Any serious adverse event that is fatal, immediately life-threatening or permanently (or significantly) disabling and requires hospitalization will be separately documented.

d) Plan for AE reporting to IRB

Planned reporting at the regular DSM meetings.

- All AE will be reported to the DSM committee every six months. In addition, the lab results from each new subject and any abnormal liver enzyme values will be reported after consultation with our pharmacist who has the randomization codes.

Serious AE reporting.

- All serious adverse events will be immediately reported to the PIs. The PIs and designated research team will generate a serious adverse event report. The report will include a description of the event, when and how it occurred, as well as any official chart records or documentation to corroborate the event.
- The serious adverse events will be reported to the Medical Investigator at an expedited ad hoc meeting.
- The report will be then immediately forwarded to the IRB (<5 days of the event).

e) Annual safety reports. Based on the documentation from the DSM committee meetings compiled by the Independent Monitor, the study coordinator will prepare a report. A statement reflecting the results of the reviews with the Independent Monitor will be sent to the IRB. This report will include a list of adverse events and will address: (1) whether adverse event rates are consistent with pre-study assumptions; (2) reasons for dropouts from the study; (3) whether all participants met entry criteria; (4) whether continuation of the study is justified on the basis that additional data is needed to accomplish the stated aims of the study; and (5) conditions whereby the study might be terminated prematurely.

f) Stopping Rules - This study will be stopped prior to its completion if: (1) the intervention is associated with adverse effects that call into question the safety of the intervention; (2) difficulty in study recruitment or retention will significantly impact the ability to evaluate the study endpoints; (3) any new information becomes available during the trial that necessitates stopping the trial; or (4) other situations occur that might warrant stopping the trial. Data on subject accrual and completion rates will be synthesized and evaluated annually to determine if the study should be terminated. These data will be reviewed by the study PIs, with consultation from the study biostatistician.

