#### **IV. EXPERIMENTAL DESIGN AND METHODS**

All study visits and clinic procedures will be conducted over the course of 1 year at Pennington Biomedical Research Center (PBRC) by trained nurses and research staff in accordance with standard operating and quality control procedures approved by PBRC's Institutional Review Board (IRB). This is a between-subjects parallel study design. All women will undergo a 30% energy restriction for 8-weeks and will be randomized to an ethanol-consuming group or a non-ethanol control group at the start of the study.

Table 1: Schedule of Study Events					
Tests	SV 1	Pre-Rand Visit	CV1	Intervention wk 1- wk 8	CV 2 (wk 8)
Informed Consent/Lifestyle Interview	X				
Height (SV1 only)/Metabolic Weight/BMI, Waist and Hip Circumference, Pulse, and Blood Pressure	X		X		X
Alcohol-related questionnaires (The Short Alcohol Dependence Data, SASSI, MAST)	X			X	
Pedometer Distributed/Collected		X		X (Wk8)	
Food Record/Washout Instructions		X			
Food Record Compliance Check			X		
Medical History/ Physical/ Medications	X				
Medications/Adverse Event Report			X	X(wkly)	X
Fasting Blood Draw*	X†		X*		X*
Questionnaires (retrospective VAS)			X		X
MRI,  H-MRS, FibroScan			X		X
Physical Activity (steps/day)			X		X
Alcohol Tolerance Test		X			
Randomization			X		
Controlled Feeding Dietary Intervention				X	
Body Weight				X	

CV, Clinic Visit; SASSI, Substance Abuse Subtle Screening Inventory; MAST, Michigan Alcoholism Screening Test; VAS, Visual Analogue Scale / †Chem 15, HCG / \*Chem 26, insulin, free and total testosterone and archives

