#### 8-Week Dietary Intervention

Participants will be provided all meals that are prepared by the PBRC metabolic kitchen (5-day meal rotation) and given both verbal and written instructions as to the consumption of the

food. On weekdays, at least one meal (i.e. breakfast, lunch, or dinner) will be consumed at PBRC 3 times per week, (excluding holidays), whereas the other weekday meals will be packaged for takeout. In addition, alcohol, weekend, and holiday meals will be packaged for takeout. Participants' energy requirements will be determined from their estimated resting metabolic rate (RMR), calculated via the Mifflin-St. Jeor formula, with an activity factor of 1.5. The energy requirements will then be multiplied by 0.70 so that all participants will restrict energy needs by 30% compared to weight maintenance. Each group (control and ethanol) will have the same 30% reduction in calories and will consume the same percentage of each traditional macronutrient (20% protein, 50% carbohydrate, and 30% fat). The ethanol group will consume a 30% energy restriction diet that will also include ~2.5 standard drinks, or 35 grams of ethanol, administered as 80-proof distilled spirits (e.g. 80 proof gin, rum, vodka, whiskey, or tequila). In the United States, one "standard" drink contains roughly 14 grams of pure alcohol. Caloric differences between the spirits will be accounted for by being administered on specific days of the meal rotation so that the appropriate mixers are provided. The remaining calories (Mifflin-St. Jeor formula, with an activity factor of 1.5 multiplied by 0.70 minus the ~240 kcals from ethanol) will be consumed as 20% protein, 50% carbohydrate, and 30% fat. The control group will consume these ~240 kcal as included in the aforementioned macronutrient percentages (20% protein, 50% carbohydrate, and 30% fat).

Participants will be asked to have an in-clinic check in once per week when coming for their in-house meal. At this check a metabolic weight will be obtained, adverse events and changes in medication will also be assessed. The ethanol group will be also be administered the alcohol-related questionnaires.

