#### Participant Safety

Subjects in the ethanol group will be closely monitored and frequently assessed throughout the study to identify any signs of alcoholism. A questionnaire (The Short Alcohol Dependence Data Questionnaire) will be administered weekly to evaluate the possibility of alcohol dependency. We will also re-administer the SASSI and MAST questionnaires. Study staff will verbally correspond with the participants weekly to assess any adverse events and ascertain any undesirable changes in mood or daily routine that may be associated with alcohol consumption. The Medical Investigator will have oversight through the duration of the study.

If any participant exhibits signs of alcohol dependency issues during the study based on self-report or the weekly questionnaires, a more comprehensive assessment (i.e. interview) by trained study staff and the medical investigator will be done. The subject will be withdrawn from the study and referred to a substance abuse center for treatment.

At the end of the intervention, participants will be contacted (phone) by trained study staff at 2 weeks and 4 weeks after completion of the study in order to assess if the women have acquired any alcohol abuse and/or dependency issues. If the subject exhibits any alcohol-related issues, she will be referred to a substance abuse center for treatment.

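### Grade 1 forms of the anticipated ethanol effects get no adverse event entry, so the annual AE list mixes two severity thresholds (minor)

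*Protocol*

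**What the plan says.** The protocol's Data and Safety Monitoring Plan (DSMP), under Safety Monitoring, item b), says that AEs are "defined as expected adverse events if they are grade 2 and above in severity and unexpected side effect/events of any severity category". Under the heading on AE documentation by the study coordinator, a reported event "which meets the criteria for an adverse event will be documented as such and graded as to its attribution (alcohol relatedness) and severity". Documentation and rating are thus tied to the definition.

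The anticipated effects are in Table 2. Its row on ethanol consumption names long-term health risks and then continues: "Other risks include drowsiness, malaise, mood and behavior changes, depression, headaches, impaired coordination and judgment". Item a) of Safety Monitoring, directly before the definitions, refers to "A description of the anticipated risks (i.e. adverse events) related to the procedures" and says that they are shown in Table 2 and will go into the consent form.

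AEs are sought often. Table 1 has a row "Medications/Adverse Event Report" marked at CV1, weekly in the intervention and at CV2. The section on the 8-week dietary intervention says of the weekly clinic check: "At this check a metabolic weight will be obtained, adverse events and changes in medication will also be assessed". Neither place limits this to one arm. The Participant Safety section adds: "Study staff will verbally correspond with the participants weekly to assess any adverse events and ascertain any undesirable changes in mood or daily routine".

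Laboratory findings have their own rule: "Any out of range lab values from these tests will be recorded and reported to the PI".

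The Pre-Randomization Visit section calls headache, nausea and diarrhea on the tolerance-test night minor adverse events and has staff call the medical investigator. The annual safety report is to list AEs and to address whether their rates agree with what was assumed before the study.

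**The concern.** The severity threshold acts at documentation, not only at reporting. Staff must judge whether a symptom is expected, and whether it is grade 1 or grade 2, before an AE entry exists. If the answer is expected and grade 1, the definition leaves no AE record of the symptom, its grade or its relation to alcohol, and so nothing by which that judgement could later be checked.

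The symptoms treated this way are those that the protocol itself anticipates from ethanol, while symptoms not anticipated count from grade 1 upward. At stake is how well a 12-woman pilot can describe mild tolerability of daily ethanol under energy restriction, and what the AE rates in the annual report mean. The efficacy results are not at stake.

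**Working it through.** The protocol states no figure on this point, so there is none to reproduce. The check is to apply the definition and the documentation rule to each kind of event.

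| Event | Grade 1 | Grade 2 or above |
|---|---|---|
| Expected | not an AE: no AE entry, no relatedness rating | AE, graded and rated |
| Unexpected | AE, graded and rated | AE, graded and rated |

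Only one cell is empty. With Table 2 as the list, mild headache, drowsiness and malaise fall into it.

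**Effect on the AE total.** For one arm, let *m* be the number of grade 1 expected events, *s* the number of expected events of grade 2 or above, and *u* the number of unexpected events of any grade.

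- Events that occurred: *m* + *s* + *u*.
- Events listed as AEs: *s* + *u*.
- Omitted: *m*.

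The listed total therefore adds *s*, which starts at grade 2, to *u*, which starts at grade 1.

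**Direction.** Apply the rule identically in both arms. The difference between arms in listed AEs then falls short of the difference in all events by *m*(ethanol) − *m*(control). If ethanol raises the frequency of mild symptoms named in the ethanol row of Table 2, this term is positive and the listed excess is too small. Other expected events in Table 2, such as bruising from blood draws or claustrophobia in the scanner, are cut off too, but both arms undergo those procedures. The direction does not require the rule to be used differently by arm.

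**Size.** Putting a value on *m* needs the rate of such symptoms and the share that is grade 1. The protocol gives neither, so no number of lost entries is offered. What can be counted is the occasions on which AEs are asked about in the intervention: 7 × 8 = 56 weekly checks in the ethanol group and 5 × 8 = 40 in the control group, 96 in all. CV1 and CV2 come in addition, although the week 8 check may coincide with CV2.

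**The test night beside the definition.** The Pre-Randomization Visit section groups headache with nausea and diarrhea as minor adverse events. Table 2 names headaches but neither nausea nor diarrhea. If Table 2 is the list, a grade 1 headache is not an AE while grade 1 nausea is, although one section calls both adverse events.

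**The case against.** The strongest reply is that a lighter logging threshold for mild, anticipated effects is an explicit choice, and that nothing in the protocol requires AE entries at every grade. It can be added that every listed AE carries a severity grade and that all events of grade 2 and above are captured whether expected or not. A reader can therefore restrict the list to grade 2 and above and recover one uniform threshold. Both statements are correct, and they are the main reason why the point is minor. The uniform list, however, is obtained by discarding the mild events altogether. The missing ones cannot be restored.

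It also stands that mild effects are not wholly lost. Out-of-range laboratory values are recorded without a grade limit, changes in mood or routine are asked about weekly, and symptoms on the test night go to the medical investigator. What a mild anticipated symptom lacks is the AE entry with its grade and relatedness rating. The test-night text is an escalation instruction rather than a second definition, so the mismatch there is one of wording.

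A reader might infer two stronger points, which the protocol does not support:

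- **That 'expected' has no reference.** Item a) of Safety Monitoring stands directly before the definitions, equates anticipated risks with adverse events, and points to Table 2 and the consent form. Only a cross-reference within the definition is lacking.
- **That the definition works differently by arm**, so that a mild headache would count in a control woman and not in an ethanol woman. The definition names no arm, and no passage applies it by arm.

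**Conclusion.** The point holds as a minor one. By the protocol's own wording, grade 1 forms of the anticipated ethanol effects receive no AE entry and no relatedness rating, while unexpected events are entered at any grade. The AE list and rates in the annual safety report therefore rest on two thresholds.

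That they tend to understate mild ethanol effects rests on two assumptions: that Table 2 is what 'expected' refers to, and that daily ethanol makes the mild symptoms named there more frequent. The amount is unknown. The pre-study AE assumptions against which the report is to compare rates are not stated either, so no mismatch with them can be shown.

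No planned endpoint is affected. The stopping rule speaks of adverse effects that call the intervention's safety into question and does not depend on the AE definition.

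**What to change.** Change the DSMP so that untoward events of every grade are documented in both arms, each with severity and alcohol relatedness. Use expectedness and grade only to decide what is reported and how fast. The annual report can then show rates at any chosen threshold.

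Two smaller wording changes go with this:

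- Have the AE definition cross-refer to the Table 2 list already cited in item a) of Safety Monitoring.
- Reconcile the term for minor events in the Pre-Randomization Visit section with the definition.

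The cost is a protocol wording change and some additional AE lines at weekly checks that already take place. In 12 women over 8 weeks the number should be small, but it cannot be estimated from the protocol. No new visit, procedure or question to participants is needed.
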